6.5.1 Treatment Exposure

Duration of treatment exposure will be defined as number of days on treatment (computed as described in 6.3.6). Duration of treatment exposure will be summarized by treatment group using descriptive statistics. Duration of treatment exposure will also be categorized according to the following intervals (No exposure, 1-30, 31-182, 183-365, 366-730, 731-1095, and > 1095 days) and summarized accordingly using frequencies and percentages, by treatment group.

In addition, as a separate table, the number of subjects who had a permanent study treatment discontinuation will be summarized using frequencies and percentages, by treatment group.

Information on treatment exposure, study treatment interruption and study treatment discontinuation will also be listed.

6.5.2 Adverse Events and Serious Adverse Events

In general, treatment groups will be compared with respect to the incidence of AEs and SAEs overall and by body system.

6.5.2.1 Adverse Events

Summary statistics will be presented by treatment arm for all treatment-emergent adverse events (TEAEs) and, in addition, by intensity [Mild, Moderate, Severe, Life-Threatening] and relationship to study medication as judged by the investigator [Not Related, Related]. A treatment-emergent AE will be defined as an AE with onset date on or after the date of randomization. For subjects experiencing repeated episodes, only the most severe episode and the episode with the strongest relationship will be reported. Summary statistics will include number and incidence of events where incidence of an event within a treatment group will be determined as the simple proportion of subjects in the group experiencing the event.

Adverse events will be grouped and summarized by system organ class and preferred term as defined by the latest version of the Medical Dictionary for Regulatory Activities (MedDRA, version 19.1 or higher).

All AEs will be included in subject data listings but only treatment-emergent AEs will be summarized.

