#### 4.5 Criteria for Premature Study Medication Discontinuation

Based on extensive experience with dalcetrapib 600 mg/day in previous Phase III trials, dalcetrapib is well tolerated. However, if tolerability leads to considerations of study medication discontinuation, it is preferable to titrate the patient down to 300 mg/day (1 tablet per day instead of 2 tablets per day) at the investigator's discretion rather than discontinuing study medication. Any dose changes will be recorded in the eCRF. Subjects stopping study medication should be followed until the end of the study with the same procedures and not be withdrawn unless the subject refuses to give further information.

Additionally, for any subject prematurely discontinuing study medication, assessments will be conducted every 6 months for the collection of study endpoints and concomitant medications. Every effort must be made to obtain endpoint data through the duration of the trial, even if the patient discontinues study medication.

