#### 8.2.2.4 Safety Analysis Population

All subjects who received at least one dose of treatment will be included in the safety analysis population. Subjects will be assigned according to the true treatment received for analysis purposes.

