6.4.5.4 Analysis Based on Exposure to Study Treatment

Subjects who were off study treatment for an extended period of time may have a different risk profile as compared to the ITT population and two additional analyses will be performed to investigate the effect of exposure to study treatment.

- 1) Excluding events occurring 14 days after last dose of study treatment in subjects who discontinued study treatment prematurely

The time from randomization to first occurrence of any component of the composite endpoint of CV death, resuscitated cardiac arrest, non-fatal MI or non-fatal stroke (primary endpoint) will be calculated as number of days between randomization and event in subjects with an event and event-free subjects will be censored at the date they were last known to be event free (as for the primary analysis). However, in subjects who discontinued treatment prematurely (i.e. who reported a study treatment discontinuation on the *Treatment Inter/ Disc* Form of the eCRF), any event occurring 14 days or more after date of last dose will not count as an event. The analysis will be conducted on all randomized subjects (no subject excluded) using the same model as described in section 6.4.1.

- 2) Excluding subjects who discontinued study treatment prematurely and who had their first event at least 14 days after last dose of study treatment

The time from randomization to first occurrence of any component of the composite endpoint of CV death, resuscitated cardiac arrest, non-fatal MI or non-fatal stroke (primary endpoint) will be calculated as number of days between randomization and event in subjects with an event and event-free subjects will be censored at the date they were last known to be event free (as for the primary analysis). However, subjects who discontinued treatment prematurely (i.e. who reported a study treatment discontinuation on the *Treatment Inter/ Disc* Form of the eCRF) and who had a first event occurring 14 days or more after last dose will be excluded. The analysis will not be conducted on all randomized subjects since some would be excluded but it will use the same model as described in section 6.4.1.

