6.5 Safety Analysis

All safety parameters will be summarized and presented in tables based on the ITT population.

For the evaluations of adverse events and general laboratory data described below, neither tests of hypotheses nor estimates of treatment effects will be reported, unless otherwise specified. It is, however, anticipated that in some instances there will be numerical treatment differences in the reported summary statistics that are either of interest or concern; in these instances, more extensive exploratory statistical analyses may be performed. The scope of the analyses cannot be determined a priori, but would be expected to include standard regression methods for estimating relative risks such as odds and hazard ratios.

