6.5.2.2 Serious Adverse Events

SAEs will be summarized similarly to all TEAEs and presented in a subject data listing.

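### SAP 6.5.2.1 calls every adverse event after randomization treatment-emergent, whatever the exposure, and the plan text describes no on-treatment AE or SAE table

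*SAP*

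**What the plan says.** SAP 6.5.2.1 defines the events to be tabulated: "A treatment-emergent AE will be defined as an AE with onset date on or after the date of randomization". It adds that "All AEs will be included in subject data listings but only treatment-emergent AEs will be summarized", and that "incidence of an event within a treatment group will be determined as the simple proportion of subjects in the group experiencing the event". Section 6.5.2.2 carries this over to serious events: "SAEs will be summarized similarly to all TEAEs and presented in a subject data listing".

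The denominator is set in SAP 6.5: "All safety parameters will be summarized and presented in tables based on the ITT population". The protocol had another safety set (8.2.2.4): "All subjects who received at least one dose of treatment will be included in the safety analysis population", grouped by the treatment actually received. SAP section 1 says that the SAP prevails where the two differ.

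Follow-up continues off drug. Protocol 4.5 says "Subjects stopping study medication should be followed until the end of the study with the same procedures", and Protocol 7.2.1 has adverse events collected from randomization to trial completion.

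For efficacy, the SAP does look at exposure. In one analysis in 6.4.5.4, for subjects who discontinued early, "any event occurring 14 days or more after date of last dose will not count as an event". That section concerns only the primary composite.

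**The concern.** The term treatment-emergent normally tells a reader that an event arose during, or shortly after, exposure. Here collection starts at randomization, so every collected event meets the definition and the rule that only such events are summarized filters nothing. An event long after the last dose counts the same as one on drug. So does an event in a subject who never took a tablet, if such subjects are in the tables. Protocol 8.2.2.2 puts all randomized subjects in the ITT population, and the exposure table in SAP 6.5.1 has a category for no exposure.

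If a harm exists only while the drug is taken, off-drug time adds background events to both arms and pulls the ratio toward 1. In safety that is the unwelcome direction. SAP 6.5 plans no tests or effect estimates for adverse events and makes further analysis depend on a numerical difference being noticed, so a reduced contrast could be passed over.

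**Working it through.** **The plan's own figures.** The documents give no discontinuation rate and no adverse event rate, so there is no figure on this point to reproduce. The one design figure, 582 events, does reproduce: 4 × (1.960 + 1.036)² / (ln 0.78)² = 582. It has no bearing here.

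**Assumed inputs.** Follow-up T = 3 years; placebo incidence 3% over T; exponential discontinuation reaching d = 10%, 20% or 30%, equal in both arms; on-drug hazard ratio R = 1.5 or 2.0; harm ending 14 days after the last dose. From the SAP: 6149 randomized 1:1, about 3074 per arm.

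**Formulas.** Background hazard h = −ln(0.97)/3 = 0.01015 per year. Discontinuation hazard = −ln(1 − d)/3. Let s be the time from randomization to last dose plus 14 days, capped at 3 years.
- Counted to study end: proportion = mean of 1 − exp(−hRs − h(3 − s)).
- Counted to last dose plus 14 days: proportion = mean of 1 − exp(−hRs).
- Placebo uses R = 1.

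**Results, equal discontinuation.**

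| R | d | Risk ratio to study end | Risk ratio with cut | Risk difference, end / cut (points) |
|---|---|---|---|---|
| 1.5 | 10% | 1.47 | 1.49 | 1.39 / 1.39 |
| 1.5 | 20% | 1.44 | 1.49 | 1.32 / 1.32 |
| 1.5 | 30% | 1.41 | 1.49 | 1.24 / 1.24 |
| 2.0 | 10% | 1.92 | 1.97 | 2.77 / 2.77 |
| 2.0 | 20% | 1.87 | 1.97 | 2.62 / 2.62 |
| 2.0 | 30% | 1.82 | 1.97 | 2.46 / 2.47 |

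The cut gives 1.49 and not 1.50 only because a ratio of proportions is slightly smaller than the hazard ratio.

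**Hand check.** The off-drug share of time is f = 1 − d/(−ln(1 − d)). At d = 20% this is 1 − 0.2/0.2231 = 0.104, or 0.101 after the 14-day lag. The diluted ratio is then 1.489 − 0.489 × 0.101 = 1.44, as in the table.

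**Other incidences.** For R = 1.5, a placebo incidence of 1% gives 1.47 to 1.42 (1.50 with the cut), and 10% gives 1.44 to 1.39 (1.46 with the cut).

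**Power, as an index only, since no test is planned.** At R = 1.5 and 3% incidence it is 0.83, 0.79 and 0.74 to study end, against 0.84, 0.82 and 0.80 with the cut.

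**Unequal discontinuation, R = 1.5, 3% incidence.**

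| Stopping, placebo / dalcetrapib | Risk ratio to study end | Cut, proportions | Cut, rates per exposure time |
|---|---|---|---|
| 20% / 20% | 1.44 | 1.49 | 1.49 |
| 20% / 30% | 1.41 | 1.40 | 1.49 |
| 20% / 40% | 1.39 | 1.31 | 1.49 |

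A cut table of proportions can therefore show less harm than the existing table. If person-time also stops at the first event, the rate ratio is 1.50 in all three rows.

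**The case against.** The strongest reply is that the existing rule is a legitimate on-study count. It matches the collection period, respects randomization, and keeps harm that appears late or persists after stopping, part of which an on-treatment cut would lose. That stands, and it is why the existing tables should remain.

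The SAP also has partial substitutes: tables by investigator-judged relatedness, events leading to drug withdrawal, exposure and permanent discontinuation by arm, full listings, and room for exploratory safety work. The DSMB sees unblinded safety data. Section 6.4.5.4 gives an exposure-based view of the gravest cardiovascular events, which Protocol 7.1.1.4 largely exempts from SAE reporting. These reduce the gap but do not close it. Relatedness is a judgement, the withdrawal table holds only events that caused stopping, the exposure table is not linked to events, and 6.4.5.4 covers one composite.

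Three stronger readings are tempting, and the documents do not support them:
- **That any harm is diluted.** Only harm confined to time on drug is, and only on the relative scale.
- **That no on-treatment table exists.** SAP section 7 leaves the list of tables to the Table Shells, which were not supplied, so the absence is shown for the SAP and protocol text only.
- **That starting at randomization distorts the tables.** Drug is dispensed at the randomization visit, so the gap to first dose should normally be short.

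Dilution may also be smaller than modelled. SAP 2.1 says that subjects who stop and decline visits are phoned every 6 months to collect endpoints, so their off-drug adverse events may be less fully recorded.

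**Conclusion.** The point holds in a limited form. The definition makes treatment-emergent mean on-study, and the supplied text offers no on-treatment view of adverse events or SAEs, although it offers one for the primary endpoint. The likely effect is modest: 1.5 reads as 1.47 to 1.41, and 2.0 as 1.92 to 1.82, with almost no change in the risk difference.

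These figures rest on assumed follow-up, incidence and equal discontinuation of 10% to 30%, with constant hazards and full recording of events off drug. None of these rates is in the documents. The presence of never-dosed subjects is inferred from Protocol 8.2.2.2 and the no-exposure category; the text of SAP 3.2 was not available for this check.

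A reader might infer that the safety tables conceal harm or are invalid. They do not show that: they answer an on-study question under an on-treatment name. This is a cheap improvement, not a flaw that threatens the safety conclusions.

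**What to change.** 1. Keep the randomization-to-end AE and SAE tables in the ITT population and label them on-study.
2. Add on-treatment AE and SAE tables in subjects with at least one dose, counting onset from first dose to within 14 days after last dose. Reserve the term treatment-emergent for these. State the boundary day: the efficacy rule in 6.4.5.4 drops events at 14 days or more. Only the 14-day convention is borrowed, since that analysis is not an onset window.
3. Report exposure-adjusted incidence rates (first events divided by person-time at risk) beside the proportions, so that unequal stopping does not drive the comparison. Say whether recorded interruptions are subtracted; SAP 6.3.6 notes that only those over 7 days are captured.
4. Carry the change into the Table Shells, or confirm that they already contain such tables.

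The cost is one extra set of descriptive tables. AE onset dates (SAP 5.1) and first- and last-dose dates (SAP 6.3.6) are already collected, so no new data are needed.

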6.5.2.2 Serious Adverse Events

SAEs will be summarized similarly to all TEAEs and presented in a subject data listing.

6.5.2.3 Adverse Events Leading to Premature Drug or to Premature Study Withdrawal

Adverse events leading to premature drug withdrawal and adverse events leading to premature study withdrawal will be summarized similarly to all TEAEs and presented in a subject data listing.

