#### 6.1.1 Dose Modifications and Delays

In the event of a subject forgetting to take drug with their largest meal that day, they can take the study drug later in the day and return to their regular schedule the next day. In the event of a subject not taking drug on a given day, he or she should not take more than the daily dose on the following day.

Temporary interruptions of study medication are allowed. Interruptions of study medication for longer than 14 days need approval of the sponsor whenever possible. In the event of a subject experiencing intolerable adverse events considered related to study medication by the investigator, the investigator should consider decreasing the dose to one tablet once daily before interrupting or permanently discontinuing study medication.

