#### 8.2.5 Safety Analyses

All safety parameters will be summarized and presented in tables based on the safety population.

For the evaluations of adverse events and general laboratory data described below, neither tests of hypotheses nor estimates of treatment effects will be reported. It is however anticipated that in some instances there will be numerical treatment differences in the

reported summary statistics that are either of interest or concern; in these instances, more extensive exploratory statistical analyses may be performed. The scope of the analyses cannot be determined a priori; but would be expected to include standard regression methods for estimating relative risks such as odds and hazard ratios.

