#### 8.2.5.1 Adverse Events

Treatments will be examined with respect to the incidence of adverse events, serious adverse events (SAEs) and adverse events leading to premature study withdrawal or dose modifications.

Summary statistics will be presented for all treatment-emergent events and, in addition, by intensity and relationship to study medication as judged by the investigator. In the latter instances, for subjects experiencing repeated episodes, only the most severe episode and the episode with the strongest relationship will be reported. Summary statistics will include number and incidence of events where incidence of an event within a treatment group will be determined as the simple proportion of subjects in the group experiencing the event.

Adverse events will be grouped and summarized by body system as defined by the latest version of the Medical Dictionary for Regulatory Activities (MedDRA), following classification of investigator assessments into MedDRA preferred terms.

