STATISTICAL ANALYSIS PLAN

Protocol number: DAL-301

PHASE III, DOUBLE-BLIND, RANDOMIZED PLACEBO-CONTROLLED STUDY TO EVALUATE THE EFFECTS OF DALCETRAPIB ON CARDIOVASCULAR (CV) RISK IN A GENETICALLY DEFINED POPULATION WITH A RECENT ACUTE CORONARY SYNDROME (ACS): THE dal-GenE TRIAL

DAL-GENE

Date of Final Statistical Analysis Plan:	05-NOV-2019
Amendment No. 1 :	15-MAR-2021
Amendment No. 2 :	10-JUN-2021
Amendment No. 3 :	07-JUL-2021

Prepared by:

[name], M.Sc.
Senior Biostatistician
Montreal Health Innovations Coordinating Center (MHICC)
[name]
[name]
[contact] [name] / [contact]

Confidentiality Statement:

The information contained in this document is the property of DalCor Pharmaceuticals and may not be disclosed to others without authorization from DalCor Pharmaceuticals.

Version	Date (DD-MMM-YYYY)	Author	Summary of Changes
Amendment 1	15-MAR-2021	[name]	
Section 6.4.5.2 (Sensitivity Analysis and Robustness Checks) 4) Add sensitivity analysis taking into account the adjudicated primary efficacy endpoints collected between the end of study visit and the 14-day safety follow-up.
 
Section 6.4.5.3 (Analysis Following the Initiation of the COVID-19 Pandemic): Add new section for sensitivity analyses to the COVID-19 pandemic.
 
Section 6.4.5.4 (Analysis Based on Exposure to Study Treatment): Add new section for sensitivity analyses to evaluate the effect of exposure to study treatment.
 
Section 6.5.2.3 (Adverse Events Leading to Premature Drug or to Premature Study Withdrawal): Replace “Adverse events leading to premature study withdrawal or dose modification” by “Adverse events leading to premature drug withdrawal” and “Adverse events leading to premature study withdrawal”.
 
Section 6.5.6 (COVID-19 Outbreak Impact): Add new section on impact of COVID-19.
 
Correction of typos throughout the text.

Amendment 2	10-JUN-2021	[name]	
Section 3.2 (Intent-To-Treat (ITT) Population): Add subject numbers who will be excluded from the ITT.

Amendment 3	07-JUL-2021	[name]	
Section 6.4.1 (Primary Analysis): Correct the discrepancy between the level of the confidence interval for the hazard ratio and the significance level of the test. The correct level is 95% to match the 0.05 significance level of the primary analysis.

TABLE OF CONTENTS

List of Abbreviations	7
1. Introduction	8
2. Study Description	8
2.1 Study Design	8
2.2 Study Objectives	10

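### SAP 6.5.2.3 drops the protocol's summary of AEs leading to dose modification, and no other available SAP section shows dose reductions

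*SAP*

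**What the plan says.** Protocol 8.2.5.1 lists what the arms will be examined on: AEs, SAEs and "adverse events leading to premature study withdrawal or dose modifications". Protocol 8.2.5 adds that safety parameters go into tables.

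SAP 6.5.2.3 reads: "Adverse events leading to premature drug withdrawal and adverse events leading to premature study withdrawal will be summarized similarly to all TEAEs". Dose modification is not mentioned. SAP section 1 gives the SAP precedence where it differs from the protocol.

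Two protocol sections make dose reduction a foreseen response to intolerance. Section 4.5 states that "it is preferable to titrate the patient down to 300 mg/day" rather than discontinue, at the investigator's discretion. Section 6.1.1, on intolerable AEs judged related to study drug, says "the investigator should consider decreasing the dose to one tablet once daily before interrupting or permanently discontinuing study medication". Section 4.5 also requires the data: "Any dose changes will be recorded in the eCRF".

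On exposure, SAP 6.5.1 summarises days on treatment and tabulates permanent discontinuations. It then says "Information on treatment exposure, study treatment interruption and study treatment discontinuation will also be listed". SAP 6.3.6 defines compliance as days on drug divided by days in study and notes that only interruptions over 7 days are captured.

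**The concern.** The two SAP summaries pick up an AE only if it ended in withdrawal from drug or from the study. The protocol expects some intolerance to be managed short of that. A subject whose dose is reduced because of an AE, and who then stays on the lower dose, appears in neither summary.

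At stake is one planned safety comparison: how often, in each arm, an AE was troublesome enough to change the dose. Long-term safety is a stated objective in both documents. In a trial where reduction is preferred to stopping, withdrawal counts alone are an incomplete measure of tolerability. A reader who sees similar withdrawal counts would have no planned output showing whether dose reductions were also similar.

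**Working it through.** The documents state no figure on this point that could be reproduced. The check is a comparison of texts, one line of arithmetic on exposure, and a test of whether the size can be derived.

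**1. Current protocol against current SAP**

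| Item | Protocol | SAP |
|---|---|---|
| AEs leading to study withdrawal | 8.2.5.1: yes | 6.5.2.3: yes |
| AEs leading to drug withdrawal | 8.2.5.1: not named | 6.5.2.3: yes |
| AEs leading to dose modification | 8.2.5.1: yes | none found |
| Dose reductions | 4.5: recorded in eCRF | no table or listing described |
| Interruptions | 6.1.1: allowed | 6.5.1: listed; 6.3.6: subtracted from days if over 7 days |
| Permanent discontinuation | 4.5: subject followed to study end | 6.5.1: tabulated by arm |

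The gap lies between two texts in force and does not depend on the amendment log. The log adds only that Amendment 1 replaced "Adverse events leading to premature study withdrawal or dose modification" with the two withdrawal items. It gives no reason.

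**2. Following one subject through the planned outputs**

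Take a subject with a related, non-serious AE who goes to one tablet daily and never stops.

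- SAP 6.5.2.1: the AE is counted by arm, intensity and relationship, and it is listed.
- SAP 6.5.2.3: the AE is in neither summary.
- SAP 6.5.1: the subject is not a permanent discontinuation and has no interruption. The dose change is not among the items listed.
- AE record: protocol 5.8.1 and SAP 5.1 name onset and end dates, intensity, relationship and outcome. Action taken is named only for SAEs, in protocol Appendix 2. The listing as described would therefore not show that this AE led to a dose change.

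**3. Exposure and compliance for the same subject**

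Let the subject be in the study for N days, dosing from randomization to completion with no interruption.

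- Compliance under SAP 6.3.6 = N / N × 100 = 100%.
- Exposure under SAP 6.5.1 = N days, the same as for a subject on full dose.
- If the lower dose applies throughout, tablets taken relative to the assigned two per day = (1 × N) / (2 × N) × 100 = 50%.

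A count in days cannot show a dose reduction.

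**4. Size**

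Let p be the proportion of an arm with an AE leading to any dose action, and f the share of those managed without a permanent stop. The drug-withdrawal summary then shows p(1 − f), and p × f is missing from it. The between-arm difference it shows is p_D(1 − f_D) − p_P(1 − f_P), where D is dalcetrapib and P is placebo. The documents give neither p nor f for either arm.

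Purely as an assumed range, take p = 5% to 10%, f = 10% to 50%, and 6149 / 2 = 3074.5 subjects per arm:

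- low end: 3074.5 × 0.05 × 0.10 ≈ 15 subjects per arm missing from the summary
- high end: 3074.5 × 0.10 × 0.50 ≈ 154 subjects per arm missing from the summary

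These values show the mechanism and are not estimates. Nor can the effect on the between-arm difference be signed. With equal f in both arms the difference shrinks by the factor (1 − f). With unequal f it can move either way.

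**The case against.** The strongest reply is that no AE disappears. SAP 6.5.2.1 summarises every treatment-emergent AE by arm, system organ class, preferred term, intensity and relationship, and lists all AEs. The events that 6.1.1 addresses, intolerable and judged related, enter the related-AE and intensity summaries whatever happened to the dose. This stands. A reader might infer that tolerability problems will be under-reported, but the documents do not support that. What is lost is the identification of an AE as having led to a dose change.

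A reader might also infer that the protocol orders sites to reduce before stopping, or steers them towards interruption. It does neither. Reduction is preferable, at the investigator's discretion, and to be considered. Interruption is merely allowed, and 6.1.1 places reduction ahead of it.

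The SAP change was openly logged, and it brought a gain: AEs leading to drug withdrawal now have their own summary, which protocol 8.2.5.1 does not name. That is fair, but adding it did not require removing dose modification.

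SAP 6.5 permits further analysis where reported summaries show differences of interest. This helps only if the quantity is summarised in the first place.

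Finally, SAP section 7 leaves the list of outputs to a Table Shells document that is not available here. It may contain such a table. If so, the SAP text should say so.

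**Conclusion.** The point holds in a limited form. A safety summary that the current protocol plans is absent from the SAP that overrides it, and no available SAP section replaces it. AEs managed by dose reduction remain in the general AE tables and listings but cannot be identified as dose-limiting, and counts in days treat a subject on one tablet as fully exposed. The planned between-arm view of this tolerability measure is lost.

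The size cannot be estimated from the documents, and no bias in a stated direction can be claimed. The efficacy analyses do not depend on this. The conclusion rests on two assumptions: that the Table Shells contain no such output, and that drug withdrawal in SAP 6.5.2.3 means a permanent stop. It is a cheap improvement worth making.

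**What to change.** Keep both withdrawal summaries in SAP 6.5.2.3 and make two additions.

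1. In SAP 6.5.2.3, restore a descriptive by-arm summary of AEs leading to dose modification, for AEs where the eCRF records the link to the dose change.
2. In SAP 6.5.1, add a by-arm count of subjects with any recorded dose reduction and of subjects with any recorded interruption over 7 days.

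Do not attribute a dose change to an AE by date alone unless the table labels the attribution as inferred. If the sponsor prefers to leave the summary out, the SAP should give the reason and protocol 8.2.5.1 should be aligned.

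The cost is one or two extra descriptive tables. Protocol 4.5 already requires dose changes to be recorded, so the counts in item 1's companion table (item 2) need no new data collection. The downside is that AE attribution may be incomplete for non-serious AEs, because an action-taken field is named only for SAEs. The counts in SAP 6.5.1 do not depend on that link.
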